4.4 Diet/Activity/Other Considerations

4.4.1 Diet

Subjects should maintain a normal diet unless modifications are required to manage an AE such as diarrhea, nausea or vomiting. Diet should exclude grapefruit and grapefruit juice.

4.4.2 Contraception

Nivolumab and axitinib may have adverse effects on a fetus in utero. Furthermore, it is not known if these agents have transient adverse effects on the composition of sperm.

For this trial, male subjects will be considered to be of non-reproductive potential if they have azoospermia (whether due to having had a vasectomy or due to an underlying medical condition).

Female subjects will be considered of non-reproductive potential if they are either:

(1) postmenopausal (defined as at least 12 months with no menses without an alternative medical cause; in women < 45 years of age a high follicle stimulating hormone (FSH) level in the postmenopausal range may be used to confirm a post-menopausal state in women not using hormonal contraception or hormonal replacement therapy. In the absence of 12 months of amenorrhea, a single FSH measurement is insufficient.);

OR

(2) have had a hysterectomy and/or bilateral oophorectomy, bilateral salpingectomy or bilateral tubal ligation/occlusion, at least 6 weeks prior to screening;

OR

(3) has a congenital or acquired condition that prevents childbearing.

Female and male subjects of reproductive potential must agree to avoid becoming pregnant or impregnating a partner, respectively, while receiving study drug and for 5 months after the last dose of study drug for females and 7 months for males by complying with one of the following:

(1) practice abstinence[†] from heterosexual activity;

OR

(2) use (or have their partner use) acceptable contraception during heterosexual activity.

Acceptable methods of contraception are[‡]:

Single method (one of the following is acceptable):

- intrauterine device (IUD)
- vasectomy of a female subject's male partner
- contraceptive rod implanted into the skin

Combination method (requires use of two of the following):

- diaphragm with spermicide (cannot be used in conjunction with cervical cap/spermicide)
- cervical cap with spermicide (nulliparous women only)
- contraceptive sponge (nulliparous women only)
- male condom or female condom (cannot be used together)
- hormonal contraceptive: oral contraceptive pill (estrogen/progestin pill or progestinonly pill), contraceptive skin patch, vaginal contraceptive ring, or subcutaneous contraceptive injection

†Abstinence (relative to heterosexual activity) can be used as the sole method of contraception if it is consistently employed as the subject's preferred and usual lifestyle and if considered acceptable by local regulatory agencies and ERCs/IRBs. Periodic abstinence (e.g., calendar, ovulation, sympto-thermal, post-ovulation methods, etc.) and withdrawal are not acceptable methods of contraception.

Subjects should be informed that taking the study medication may involve unknown risks to the fetus (unborn baby) if pregnancy were to occur during the study. In order to participate in the study subjects of childbearing potential must adhere to the contraception requirement (described above) from the day of study medication initiation (or 14 days prior to the initiation of study medication for oral contraception) throughout the study period up to 120 days after the last dose of trial therapy. If there is any question that a subject of childbearing potential will not reliably comply with the requirements for contraception, that subject should not be entered into the study.

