	1.5 ULN			
ACT (CCOT) = 1 ALT (CCDT)	≤ 2.5 X ULN OR			
AST (SGOT) and ALT (SGPT)	≤ 5 X ULN for subjects with liver metastases			
Coagulation				
International Normalized Datic (IND) or	≤1.5 X ULN unless subject is receiving anticoagulant therapy			
International Normalized Ratio (INR) or	as long as PT or PTT is within therapeutic range of intended use			
Prothrombin Time (PT)	of anticoagulants			
Astivated Partial Thrombonlastin Time	≤1.5 X ULN unless subject is receiving anticoagulant therapy			
Activated Partial Thromboplastin Time	as long as PT or PTT is within therapeutic range of intended use			
(aPTT)	of anticoagulants			
*Creatinine clearance should be calculated per institutional standard.				

- 9. Patients with brain metastases are permitted if they are asymptomatic or previously treated with CNS directed therapy with stable CNS disease for at least 2 weeks. Stable is defined as asymptomatic or not progressing on imaging.
- 10. Female patients of childbearing potential must have a negative urine or serum pregnancy test within 7 days from the time of registration. Also, within 24 hours prior to receiving the first dose of study medication then every 4 weeks while on treatment.
- 11. Female subjects of childbearing potential should be willing to use 2 methods of birth control or be surgically sterile or abstain from heterosexual activity for the course of the study and for 5 months after the last dose of study medication. Subjects of childbearing potential are those who have not been surgically sterilized or have not been free from menses for > 1 year.
- 12. Male subjects should agree to use an adequate method of contraception starting with the first dose of study therapy through 7 months after the last dose of study therapy.

Note: Abstinence is acceptable if this is the usual lifestyle and preferred contraception for the subject.

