- 17. Has active autoimmune disease that has required systemic treatment in the past 2 years (i.e. with use of disease modifying agents, corticosteroids or immunosuppressive drugs). Replacement therapy (e.g., thyroxine or physiologic corticosteroid replacement therapy for adrenal or pituitary insufficiency, etc.) is not considered a form of systemic treatment
- 18. Has a history of (non-infectious) pneumonitis that required steroids or current pneumonitis.
- 19. Has an active infection requiring systemic IV antibiotic therapy.
- 20. Has had any of the following within the past 6 months
 - Myocardial infarction or unstable angina
 - Ventricular arrythmia
 - Acute decompensated heart failure
 - Cerebrovascular accident
 - Hypertensive emergency requiring ICU admission

- 21. Presence of a disorder that may impact absorption of axitinib, such as inability to take oral medication, requirement for IV alimentation, prior gastric resection, treatment for active peptic ulcer confirmed by endoscopy within the past 3 months, active GI bleed, malabsorption syndrome.
- 22. Has a history or current evidence of any condition, therapy, or laboratory abnormality that might confound the results of the trial, interfere with the subject's participation for the full duration of the trial, or is not in the best interest of the subject to participate, in the opinion of the treating investigator.
- 23. Has known psychiatric or substance abuse disorders that would interfere with cooperation with the requirements of the trial.
- 24. Is pregnant or breastfeeding or expecting to conceive or father children within the projected duration of the trial, starting with the pre-screening or screening visit through 5 months after the last dose of trial treatment for females and 7 months after the last dose of trial treatment for males.
- 25. Has a known history of Human Immunodeficiency Virus (HIV) (HIV 1/2 antibodies) if the CD4 count is less than 350 mm3 or serum HIV viral load is < 25,000 IU/mL.
- 26. Has a known history of or is positive for hepatitis B (hepatitis B surface antigen [HBsAg] reactive) or hepatitis C (hepatitis C virus [HCV] RNA [qualitative] is detected). Note: Without known history, testing only needs to be performed if there is clinical suspicion for Hepatitis B or C.
- 27. Is currently incarcerated or otherwise detained.
- 28. Has received a live vaccine within 30 days of planned start of study therapy.

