5.2.1 Reporting of Pregnancy and Lactation to the Sponsor

Although pregnancy and lactation are not considered adverse events, it is the responsibility of investigators or their designees to report any pregnancy or lactation in a subject (spontaneously reported to them) that occurs during the trial.

Pregnancies and lactations that occur after the consent form is signed but before treatment allocation/randomization must be reported by the investigator if they cause the subject to be excluded from the trial, or are the result of a protocol-specified intervention, including but not limited to washout or discontinuation of usual therapy, diet, placebo treatment or a procedure.

Pregnancies and lactations that occur from the time of treatment allocation/randomization through 120 days following cessation of Sponsor's product, or 100 days following cessation of treatment if the subject initiates new anticancer therapy, including during at least 5 half-lives after product administration, whichever is earlier, must be reported by the investigator. All reported pregnancies must be followed to the completion/termination of the pregnancy. Pregnancy outcomes of spontaneous abortion, missed abortion, benign hydatidiform mole, blighted ovum, fetal death, intrauterine death, miscarriage and stillbirth must be reported as

serious events (Important Medical Events). If the pregnancy continues to term, the outcome (health of infant) must also be reported.

Such events must be reported within 24 hours to the Sponsor and within 24 hours (1 business day) to BMS and Pfizer Global Safety.

5.2.2 Immediate Reporting of Adverse Events to the Sponsor and to BMS and Pfizer

If any SAE meets FDA/IRB reporting guidelines, we would transfer the information onto a Medwatch form for submission to BMS and/or Pfizer.

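### Section 4.4.2 ends women's post-treatment contraception at both 5 months and 120 days; the 120-day limit is about a month too short

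*Combined protocol and SAP*

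**What the plan says.** Section 4.4.2 (Contraception) opens with the reason for the rule: "Nivolumab and axitinib may have adverse effects on a fetus in utero". It then requires subjects of reproductive potential to avoid pregnancy, or causing one, during treatment and "for 5 months after the last dose of study drug for females and 7 months for males".

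The last paragraph of the section returns to the duty. It says that "subjects of childbearing potential must adhere to the contraception requirement (described above"), starting when study medication starts (14 days earlier for oral contraception) and continuing "throughout the study period up to 120 days after the last dose of trial therapy".

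Two eligibility criteria cover the same period for women:

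- Section 4.1.1, inclusion criterion 11, asks for two methods of birth control, surgical sterility or abstinence "for the course of the study and for 5 months after the last dose of study medication". It also defines the group: "Subjects of childbearing potential are those who have not been surgically sterilized or have not been free from menses" for more than a year.
- Section 4.1.2, exclusion criterion 24, excludes anyone who is pregnant or expects to conceive "through 5 months after the last dose of trial treatment for females".

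**The concern.** Both statements in 4.4.2 count from the last dose, apply to the same women and describe the same duty, yet they end it on different dates. The 120-day sentence is not background text. It is framed as a condition of taking part, it follows directly on what subjects are to be told about risk to an unborn child, and it precedes the instruction not to enter anyone who may not comply. A coordinator could reasonably counsel from it.

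What is at stake is participant protection. A woman counselled from the closing paragraph would stop contraception about a month before the date she had to accept to be eligible. No efficacy result depends on this.

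**Working it through.** There is no design figure to reproduce. The check is a comparison of the text, followed by calendar arithmetic.

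**Do the two statements cover the same thing?**

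| Place | Who | Clock starts | Ends |
|---|---|---|---|
| 4.4.2, main rule | Females of reproductive potential | Last dose | 5 months |
| 4.4.2, closing paragraph | Subjects of childbearing potential | Last dose | 120 days |
| 4.1.1, inclusion 11 | Females of childbearing potential | Last dose | 5 months |
| 4.1.2, exclusion 24 | Females | Last dose | 5 months |

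- *Population.* Inclusion 11 defines childbearing potential by sterilization and menses, so the closing paragraph is about women.
- *Duty.* The closing paragraph points back to the requirement set out above it. It restates that requirement and does not create a second one.
- *Clock.* The wording for the last dose varies slightly, but no statement separates nivolumab from axitinib, so all four start at the same point.
- *Status.* All four are current protocol text. None comes from an amendment log.

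Three statements say 5 months and one says 120 days.

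**How large is the difference?**

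Gap = (5 months in days) − 120.

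Taking 5 calendar months from every start date in 2021 to 2024 gives a minimum of 150 days, a maximum of 153 and a mean of about 152. For example:

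- 1 February to 1 July (non-leap year): 28 + 31 + 30 + 31 + 30 = 150 days.
- 1 July to 1 December: 31 + 31 + 30 + 31 + 30 = 153 days.

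So:

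- Smallest gap: 150 − 120 = 30 days, and 30/150 = 20% of the period.
- Largest gap: 153 − 120 = 33 days, and 33/153 = 22% of the period.
- Expressed in months: 120/30.44 = 3.9 months, against 5.

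**Does the meaning of a month matter?** The protocol does not define one. If a month were read as a 4-week cycle, 5 × 28 = 140 days and the gap would be 140 − 120 = 20 days. The two limits disagree on that reading too.

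**The case against.** The strongest reply is that the protocol already shows which figure governs. The 5-month period stands in the eligibility criteria, where it binds: a woman unwilling to accept it should not be entered, whatever a later sentence says. The closing paragraph defers to the requirement above it, and a site that uses the longer period satisfies both sentences. Subjects are also instructed largely through the consent form, which was not available for review, so early stopping cannot be shown to follow.

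Much of this stands. It identifies 120 days as the error, and it limits the claim about harm to what could happen if staff rely on that sentence. It does not remove the conflict. Nothing in the protocol says that the longer period prevails, and the shorter one stands in the section that staff would open for contraception advice.

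A reader might infer two stronger points, which the documents do not support:

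- *That men's 7 months is also cut to 120 days.* The closing paragraph is limited to subjects of childbearing potential, a term that the protocol defines by sterilization and menses.
- *That pregnancies will go unreported.* Section 5.2.1 also uses 120 days, or 100 days if new anticancer therapy starts. But a reporting window need not equal a contraception window. That section opens by asking investigators to "report any pregnancy or lactation in a subject (spontaneously reported to them) that occurs during the trial", and its limits carry a minimum of 5 half-lives that is not given in days. Section 4.4.3 has a separate duty to notify and follow pregnancies, without the 120-day or 100-day limit, although its reach also depends on an unstated half-life. Neither the existence nor the size of a reporting gap can be settled from this text.

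**Conclusion.** The inconsistency is real and should be corrected. For women of childbearing potential, the closing paragraph of 4.4.2 ends contraception 30 to 33 days before the main rule of that section and both eligibility criteria. The size assumes calendar months and a common last-dose date. Treating 120 days as the error rests on the three-to-one count within the protocol; the documents give no pharmacological basis for either figure.

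Confidence in the mismatch is high. Its practical reach is small: the trial plans 31 patients of both sexes, and only women of childbearing potential are concerned. The primary response-rate analysis, the two-stage design and the sample size are unaffected. The point does not extend to the contraception rule for men or to the pregnancy-reporting window.

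**What to change.** In the closing paragraph of section 4.4.2, change the end of the contraception period from 120 days to 5 months after the last dose of trial therapy, and state that this applies to female subjects. It then matches the main rule of 4.4.2, inclusion 11 and exclusion 24. The safety team should confirm 5 months before the change is made.

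The cost is a few words, with no new visit, test or data item. The consent form should be checked for the same figure; whether it needs a change cannot be judged here. Sections 4.4.3, 4.5 and 5.2.1 need no change for this point.

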4.4.3 Use in Pregnancy

If a subject inadvertently becomes pregnant while on study treatment, or may have been pregnant, including at least 5 half-lives after product administration, the subject will immediately be removed from the study and the investigational product will be permanently discontinued in an appropriate manner. The site will contact the subject at least monthly and document the subject's status until the pregnancy has been completed or terminated. The outcome of the pregnancy will be reported to the Sponsor and to BMS and Pfizer without delay and within 24 hours to the Sponsor and within 2 working days to BMS and Pfizer if the outcome is a serious adverse experience (e.g., death, abortion, congenital anomaly, or other disabling or life-threatening complication to the mother or newborn). The investigator must immediately notify [contact] of this event and complete the appropriate form in accordance with SAE reporting procedures within 24 hours of awareness of the event. Protocol-required procedures for study discontinuation and follow-up must be performed on the participant. Follow-up information regarding the course of the pregnancy, including perinatal and neonatal outcome, and where applicable, offspring information must be reported to BMS as well. Please note: if needed, a BMS pregnancy surveillance form can be provided.

The study investigator will make every effort to obtain permission to follow the outcome of the pregnancy and report the condition of the fetus or newborn to the Sponsor. If a male subject impregnates his female partner the study personnel at the site must be informed immediately and the pregnancy reported to the Sponsor and to BMS and Pfizer. Information on this pregnancy will be collected on the Pregnancy Surveillance Form. In order for Sponsor or designee to collect any pregnancy surveillance information from the female partner, the female partner must sign an informed consent form for disclosure of this information.

4.4.4 Use in Nursing Women

It is unknown whether the study drugs are excreted in human milk. Since many drugs are excreted in human milk, and because of the potential for serious adverse reactions in the nursing infant, subjects who are breast-feeding are not eligible for enrollment.

4.5 Subject Withdrawal/Discontinuation Criteria

Subjects may withdraw consent at any time for any reason or be dropped from the trial at the discretion of the investigator should any untoward effect occur. In addition, a subject may be withdrawn by the investigator or the Sponsor if enrollment into the trial is inappropriate, the trial plan is violated, or for administrative and/or other safety reasons.

A subject must be discontinued from the trial for any of the following reasons:

- The subject or legal representative (such as a parent or legal guardian) withdraws consent.
- Confirmed radiographic disease progression

Note: For unconfirmed radiographic disease progression, please see Section 5.2.2

Note: A subject may be granted an exception to continue on treatment with confirmed radiographic progression if clinically stable or clinically improved, please see Section 7.1.2.7.1

- Unacceptable adverse experiences as described in Section 5.2.1.2
- Intercurrent illness that prevents further administration of treatment
- Investigator's decision to withdraw the subject
- The subject has a confirmed positive serum pregnancy test
- Noncompliance with trial treatment or procedure requirements
- The subject is lost to follow-up
- Completed 24 months of uninterrupted treatment with nivolumab or 24 administrations of study medication, whichever is later.

Note: 24 months of study medication is calculated from the date of first dose.

• After trial discontinuation (whether due to subject withdrawal, progression, or dose limiting toxicity), patients will be seen at week 4 for follow up, and then followed once 100 days after the last day of treatment even if they start a new anticancer therapy. Patients will be contacted by phone for survival follow up for up to 5 years.

4.5.1 Discontinuation of Study Therapy after CR

Discontinuation of treatment may be considered for subjects who have attained a confirmed CR that have been treated for at least 24 weeks with nivolumab and axitinib and had at least two treatments with axitinib beyond the date when the initial CR was declared.

4.6 Clinical Criteria for Early Trial Termination

Early trial termination will be the result of the criteria specified below:

- 1. Quality or quantity of data recording is inaccurate or incomplete
- 2. Poor adherence to protocol and regulatory requirements
- 3. Incidence or severity of adverse drug reaction in this or other studies indicates a potential health hazard to subjects
- 4. Plans to modify or discontinue the development of the study drug

In the event of BMS or Pfizer deciding to no longer supply study drug(s), ample notification will be provided so that appropriate adjustments to subject treatment can be made.

5.0 TRIAL PROCEDURES

5.1 Study Flow Chart

	Baseline*	C1 +/-3 days	C2 +/-3 day	C3 +/-3 day	C4 +/-3 day	C5 +/-3 day	C6 +/-3 day	C7 +/-3 day	C8 +/-3 day	C9 +/-3 day	C10 +/-3 day	C11 +/-3 day	C12 + +/-3 day	ЕОТ	Follow up#
Informed consent	X														
Demographics	X														
Medical history	X														
Concurrent meds	X	XX									X	Х			
Physical exam	X	X	XX										X	X	
Vital signs	X	X	XX										X	X	
Performance status (ECOG)	X	XX											X	X	
CBC w/diff, plts	X	X	X	X	X	X	X	X	X	X	X	X	X	X	X
Serum chemistry ^a	X	X	X	X	X	X	X	X	X	X	X	X	X	X	X
Urine dipstick	X			х		х		х		х		Х		х	
Adverse event evaluation		XX									X	X			
Radiologic evaluation & Tumor measurements	Х	Tumor measurements will be evaluated with the first scans at week 12 (+/- 1 week). Subsequent scans will be repeated every 12 weeks (+/- 1 week). Patients with complete or partial response will have confirmation scans at least 4 and up to 12 weeks later. Documentation (radiologic) must be provided for patients removed from study for progressive disease. Brain MRI will be obtained at baseline, and will be repeated at 12 weeks if patients have known brain mets, or develop neurological symptoms**. CT scans of the brain can be utilized if MRI cannot be obtained in a timely manner per the treating physician.										Х			
B-HCG ^b	X	XX													
TSH, free T4 ^c	X		X		X		X		X		X		X	X	

Tumor bx ^d	X				X										
Research Blood draws ^e	X				X									X	
Axitinib administration ^f		X	X	X	X	X	X	X	X	X	X	X	X		
Nivolumab administration		X	X	X	X	X	X	X	X	X	X	X	X		
Microbiome sampling g	X				X							X		X	

^{*:} Baseline is within 30 days of start of treatment, except for labs (14 days).

- #: After trial discontinuation (whether due to subject withdrawal, progression, or dose limiting toxicity), patients will be seen at week 4 for follow up. Survival follow-up will be obtained at day 100 days after the last day of treatment (this can be done by phone), even if they start a new anticancer therapy. Patients will be contacted by phone for survival follow up for up to 5 years.
- **: If known to have prior brain metastases, must not have evidence of active (enlarging and/or symptomatic lesions) brain disease on MRI evaluation within 2 weeks from SRS or WBRT treatment. CT scans of the brain can be utilized if MRI cannot be obtained in a timely manner per the treating physician at baseline and also at 2 week follow up, if asymptomatic.
- a. albumin, alkaline phosphatase, total bilirubin, direct bilirubin (if total bilirubin is > ULN), bicarbonate, BUN, calcium, chloride, CPK, creatinine, fasting glucose, LDH, phosphorus, potassium, total protein, SGOT [AST], SGPT [ALT], sodium.
- b: Urine or serum pregnancy test (women of childbearing potential) (+/- 3 days). To be done at screening, within 24 hours prior to receiving the first dose of study medication and then every 4 weeks while on treatment.
- c: TSH and free T4 to be done at screening, cycle 2 and then q 8 weeks (even cycles) while on treatment (+/- 3 days).
- d: Baseline biopsy will be obtained up to 30 days prior to initiation of treatment and at C4 week 12, (+/-7 days). Patients will be treated with pimonidazole 0.5g/m2 po 16-24h before each biopsy. Biopsy at progression of disease is optional. Patients must have eligibility completed and be registered on study prior to the baseline biopsy.
- e: Research Blood draws are to be done at baseline (up to 30 days prior to initiation of therapy), cycle 4 week 12 and at progression (+/- 7 days). This includes 10 green top tubes, 2 red top tubes and an ACD yellow top tube (yellow top at baseline only).
- f: Axitinib pill counts will be reviewed and axitinib dispensed at each study visit (every 4 weeks). Patients will in addition be provided an axitinib drug diary, which should be returned at each visit.
- g. Microbiome sampling will be obtained at baseline (up to 30 days prior to initiation of therapy), cycle 4 week 12 and at progression (+/- 7 days). Samples may be brought into clinic.

The Trial Flow Chart – Section 5 summarizes the trial procedures to be performed at each visit. Individual trial procedures are described in detail below. It may be necessary to perform these procedures at unscheduled time points if deemed clinically necessary by the investigator.

